8.4.3 Sensitivity and Supplementary Analyses of the Primary Efficacy Endpoint

The same CMH analysis will be repeated based on FAS:

- Using AO data handling without any imputation as additional analysis.
- Using MI approach as additional analysis.

8.5 Secondary Efficacy Endpoints and Analyses

8.5.1 Secondary Efficacy Endpoints

The secondary efficacy endpoints are defined in Section [3.2](#).

8.5.2 Main Analyses of Secondary Efficacy Endpoints

The attributes of the estimands corresponding to the secondary efficacy endpoints are summarized in [Table 2](#).

Table 2. Summary of the Estimand Attributes of the Secondary Efficacy Endpoints

Attributes of the Estimand					
Estimand Label	Treatment	Endpoint	Population	Handling of Intercurrent Events	Statistical Summary*
Binary Secondary Endpoint	• Elsubrutinib 60 mg QD and upadacitinib 30 mg QD	Achievement of SRI-4 at Week 24.	FAS	[REDACTED]	Difference in the percentage of subjects achieving each binary secondary endpoint between groups.
	• Elsubrutinib 60 mg QD and upadacitinib 15 mg QD	Achievement of BILAG-Based Combined Lupus Assessment (BICLA) response at Week 24.			
	• Elsubrutinib 60 mg QD and upadacitinib placebo QD	Achievement of Lupus Low Disease Activity State (LLDAS) at Week 24.			
	• Elsubrutinib placebo QD and upadacitinib 30 mg QD				
	• Elsubrutinib placebo QD and upadacitinib placebo QD				
Continuous Secondary Endpoint	• Elsubrutinib 60 mg QD and upadacitinib 30 mg QD	Steroid burden, assessed as change from Baseline at Week 24.	FAS	[REDACTED]	Difference in the mean change from Baseline in Continuous endpoint between groups.
	• Elsubrutinib 60 mg QD and upadacitinib 15 mg QD				
	• Elsubrutinib 60 mg QD and upadacitinib placebo QD				
	• Elsubrutinib placebo QD and upadacitinib 30 mg QD				
	• Elsubrutinib placebo QD and upadacitinib placebo QD				

Table 2. Summary of the Estimand Attributes of the Secondary Efficacy Endpoints (Continued)

Attributes of the Estimand					
Estimand Label	Treatment	Endpoint	Population	Handling of Intercurrent Events	Statistical Summary*
Count Secondary Endpoint	
 Elsubrutinib 60 mg QD and upadacitinib 30 mg QD Elsubrutinib 60 mg QD and upadacitinib 15 mg QD Elsubrutinib 60 mg QD and upadacitinib placebo QD Elsubrutinib placebo QD and upadacitinib 30 mg QD Elsubrutinib placebo QD and upadacitinib placebo QD 	Number of mild, moderate, or severe flares per patient-year (respectively and overall) by Safety of Estrogens in Lupus Erythematosus National Assessment (SELENA) SLEDAI Flare Index (SFI), assessed by number and types of flare (mild/moderate, severe, and any) per subject through Week 24 and through Week 48.	FAS	[REDACTED]	Ratio in the mean incidence rate of mild, moderate, or severe flares per patient-year between groups.

* Note: In the event the study is partially terminated, terminated groups will be removed from the comparison.

The binary secondary endpoints will be analyzed using the same approach as that for primary endpoint as specified in Section 8.4.2. Specifically, CMH adjusting for randomization stratification factors will be used to construct the treatment difference, the associated 95% CI and p-value between treatment group comparison. The NRI-C will be the primary approach for missing data handling in the analyses of binary secondary efficacy endpoints.

All continuous endpoints will be evaluated through the change from Baseline. For continuous endpoints with multiple post-Baseline visits, the treatment effect will be assessed through Mixed-effect Model Repeated Measures (MMRM) with treatment, visit

and treatment-by-visit interaction, randomization stratification factors, and the continuous fixed covariate of baseline measurement. An unstructured variance covariance matrix will be used. For continuous endpoints with a single post-baseline visit, the treatment effect may be assessed through analysis of covariance (ANCOVA) with baseline value, treatment, and randomization stratification factors as covariates. In addition, the descriptive statistics for continuous variables will be provided including sample size, mean, standard deviation, median, minimum and maximum.

For the count endpoint (e.g., number of flares by SLENAI SFI), negative binomial regression model will be used to assess treatment effect with treatment, and randomization stratification factors as covariates.

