For the count endpoints (e.g., number of flares), negative binomial regression model will be used to assess treatment effect with treatment, visit, and stratification factors as covariates.

The Cox Proportional Hazards model will be used to assess the treatment effect for the time-to-event endpoint, i.e., time to flare.

Missing Data Imputation Definition

Censoring: For the time-to-event endpoint, i.e., time to flare, missing data will be considered as censored at the last available time for the information.

NRI-C: The NRI-C will categorize any subject who does not have an evaluation during a pre-specified visit window as a non-responder for the visit, except for missing data due to COVID-19 infection or logistical restriction, which will be handled by Multiple Imputation. In addition, subjects who prematurely discontinue from study drug will be considered as non-responders for all subsequent visits after discontinuation. Subjects will also be classified as non-responders as described in Section 5.4.

As Observed: As observed analysis will not impute values for missing evaluations, and thus a subject who does not have an evaluation on a scheduled visit will be excluded from the AO analysis for that visit. Regardless of premature discontinuation of study drug, all observed data will be used in the analysis. As observed analysis may be used for both categorical variables and continuous variables for sensitivity analysis.

Mixed-Effect Model Repeated Measurements: MMRM analysis will be conducted using a mixed-effect model for continuous variables. Data collected after study drug discontinuation or initiation of rescue treatment will not be included. The mixed model includes the categorical fixed effects of treatment, visit and treatment-by-visit interaction, main stratification factors, and the continuous fixed covariate of baseline measurement. An unstructured variance covariance matrix will be used. The parameter estimations are based on the assumption of data being missing at random and using the method of restricted maximum likelihood (REML).

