8.6 Additional Efficacy Analyses

For the annualized flare rate, a negative binomial regression model will be used with the response variable being the number of flares over the 24-week or 48-week treatment period using both OC and AO data. The model will include covariates of treatment group, and randomization stratification factors. The logarithm (to base e) of the follow-up time will be used as an offset variable in the model to adjust for subjects having different exposure times. The estimated treatment effect and the corresponding 95% CI, as well as the 2-sided p-value will be presented.

A summary of the annualized flare rate by descriptive statistics as well as a summary of the number and percentage of subjects with no flares, at least one flare, 1 flare, 2 flares, and 3 or more flares, respectively, will be presented by treatment group.

Time to event (time to first flare) is defined as number of days from the date of the first dose to the date of the first occurrence of an event. It is calculated as (date of first

occurrence of Event - date of the first dosing + 1). Subjects who discontinue from study prior to experiencing the event are censored at the time of discontinuation. Subjects who are not experiencing the event are censored at the date of last non-missing measurement of SELENA SFI. Data collected on or after the occurrence of intercurrent events as specified in Section 8.2.2 will be excluded. Pairwise comparison between each treatment group and placebo will be performed by log-rank test and Cox proportional hazards regression analysis including treatment and baseline stratification factors as covariates. Same analysis will be performed using AO data as additional analysis.

All other efficacy endpoints specified in Section 3.3 will be analyzed based on FAS using the same approach as that for secondary endpoints as specified in Section 8.5.

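### SAP 8.5.2 models the secondary SFI flare count without a time-at-risk offset, and it is unclear whether the offset in SAP 8.6 applies to it

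*SAP*

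**What the plan says.** - **Estimand.** SAP Table 2 (in 8.5.2) and Appendix D summarize the count secondary endpoint as a between-group ratio of mean incidence rates per patient-year.
- **Model in SAP 8.5.2.** For the flare count, with SFI named as the example, a negative binomial model is to assess "treatment effect with treatment, and randomization stratification factors as covariates". No offset is stated.
- **Model in Protocol 7.3.** "negative binomial regression model will be used to assess treatment effect with treatment, visit, and stratification factors as covariates". This also states no offset, and it adds a visit term.
- **Model in SAP 8.6.** "For the annualized flare rate, a negative binomial regression model will be used with the response variable being the number of flares", over 24 or 48 weeks, on both observed-case (OC) and as-observed (AO) data. Here "The logarithm (to base e) of the follow-up time will be used as an offset variable in the model", and the reason given is "to adjust for subjects having different exposure times". No flare index is named, and follow-up time is not defined.
- **Pointers between sections.** 8.5.2 does not refer to 8.6. The last sentence of 8.6 sends all other Section 3.3 endpoints back to 8.5. SAP 11.2.3 lists SFI flares per patient-year through Weeks 24 and 48 among the interim endpoints, then calls for the analysis in 8.5.
- **Time to first flare (SAP 8.6).** "Subjects who discontinue from study prior to experiencing the event are censored at the time of discontinuation". Other event-free subjects are censored at their last non-missing SFI assessment. SAP 8.3 gives one general rule: censor at the last time for which information is available.

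**The concern.** A log-link count model without an offset compares mean flare counts per subject. The estimand is a ratio of rates. The two agree only if mean time at risk is the same in the arms being compared.

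Unequal time at risk is plausible. SAP 8.2 lists rescue medication and initiation or escalation of SLE-related corticosteroid as intercurrent events, and OC data drop values on or after them. If the active arms work as hypothesized, placebo subjects should reach those events more often, so placebo would have less time in which to flare. Dropout for tolerability would push the other way.

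The text supports two models for one secondary endpoint. Which one is run should not be left open until treatment codes are known.

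**Working it through.** **The plan's own figure.** The documents give no flare rate, dropout rate or power for flares. The only power figure is for the primary endpoint (65 per arm, 25% vs 45% or 50%, two-sided alpha 0.10). It reproduces at 77.7% and 91.1% against the stated 78% and 91%, but has no bearing on this point.

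**Inputs from the documents.** 65 subjects per arm, 24 weeks for the secondary endpoint, two-sided alpha 0.10.

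**Assumptions, not in the documents.** A fraction *d* of each arm is truncated, uniformly over 24 weeks and independently of flares. *d* ranges from 10% to 40%. The simulation also takes 2 flares per year on placebo and a dispersion of 0.7.

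**Closed form.** With flare rate λ and time at risk T, the mean count in an arm is λ × E[T]. So the model without an offset estimates

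(λ_active / λ_placebo) × (E[T_active] / E[T_placebo]), with E[T] = 24 × (1 − d/2) weeks.

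Example for 30% placebo, 10% active: 24 × 0.95 = 22.8 weeks, 24 × 0.85 = 20.4 weeks, and 22.8 / 20.4 = 1.118.

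| Truncated, placebo / active | Mean weeks, placebo / active | Factor | True 0.60 becomes |
|---|---|---|---|
| 10% / 10% | 22.8 / 22.8 | 1.000 | 0.600 |
| 15% / 10% | 22.2 / 22.8 | 1.027 | 0.616 |
| 20% / 10% | 21.6 / 22.8 | 1.056 | 0.633 |
| 30% / 10% | 20.4 / 22.8 | 1.118 | 0.671 |
| 40% / 10% | 19.2 / 22.8 | 1.188 | 0.712 |
| 10% / 20% | 22.8 / 21.6 | 0.947 | 0.568 |
| 10% / 30% | 22.8 / 20.4 | 0.895 | 0.537 |

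**Simulation.** Up to 1,500 trials per row, negative binomial fit with treatment only and the dispersion held at its true value. The Monte Carlo standard error of a rejection rate near 0.10 is √(0.1 × 0.9 / 1500) ≈ 0.008.

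| Placebo / active, true ratio | Estimate, no offset | Estimate, offset | Rejection, no offset | Rejection, offset |
|---|---|---|---|---|
| 10/10, 1.00 | 0.998 | 0.997 | 0.112 | 0.107 |
| 30/10, 1.00 | 1.124 | 1.006 | 0.149 | 0.102 |
| 10/10, 0.60 | 0.597 | 0.597 | 0.622 | 0.609 |
| 30/10, 0.60 | 0.662 | 0.594 | 0.448 | 0.609 |
| 10/30, 0.60 | 0.530 | 0.591 | 0.753 | 0.611 |

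**Direction.** More truncation on placebo moves the ratio up, against the active arm. At 30/10 the excess null rejections therefore point the wrong way for a benefit claim, and power falls from 61% to 45%. More truncation on active moves the ratio down. Under the null the arms differ only in truncation, so swapping the labels gives about the same inflation at 10/30, now in favour of active.

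**Time to first flare.** This was simulated as a ratio of event rates, with SFI every 4 weeks, no SFI at discontinuation and a true ratio of 1. At 30/10, censoring at the last SFI gives 0.998 and censoring at discontinuation gives 1.018 (1.018 / 0.998 = 1.020). At 10/30 the figures are 1.005 and 0.983 (0.983 / 1.005 = 0.978). The shift is about 2% either way.

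**The case against.** The strongest reply is that SAP 8.6 already deals with this. It has the same covariates, the right offset, both time horizons, and a stated purpose of adjusting for exposure. Flares per patient-year is an annualized rate, and the estimand cannot be estimated without exposure time. On that reading only a cross-reference is missing. It is a fair reading, and it rules out saying that the plan has no offset at all. It does not settle the matter. The only endpoint in SAP Section 3 called annualized is the BILAG-based rate (3.3, item 23). The section that names the SFI count states no offset, and the interim section cites 8.5.

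The second reply is that the bias is conditional. This stands. With equal mean follow-up the factor is 1.000. Stopping study drug does not by itself end follow-up: Protocol 5.6 keeps those subjects on the visit schedule, and SAP 8.2.1 uses their data.

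Third, the handling of intercurrent events for this endpoint is blacked out, so how far flare data are cut is not visible. This stands too, and is why the sizes above are illustrations and not predictions.

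Fourth, the SAP has already dropped visit, and Protocol 7.1 defers full detail to the SAP. The Protocol term is therefore a mismatch to tidy up, not an analysis likely to be run.

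Fifth, Appendix D of the Protocol schedules an SFI at the premature discontinuation visit, so the gap between last SFI and discontinuation will often be short.

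**Conclusion.** The point holds as an inconsistency in the specification of a secondary endpoint. The model in 8.5.2, taken literally, does not estimate the estimand in Table 2. The model that does is in 8.6, with unclear scope and an undefined follow-up time. The size depends entirely on imbalance in mean follow-up: none if balanced, a factor of about 1.12 with null rejection near 0.15 at an assumed 30% placebo vs 10% active, and 0.895 with the percentages reversed. These figures assume that truncation is unrelated to flares. Because SFI itself takes treatment changes into account, that may not be so, and an offset would not correct for it.

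A reader might infer more than the documents support:
- *That reported flare rates will be biased.* This needs both a literal run of 8.5.2 and unequal follow-up.
- *That follow-up time in 8.6 runs past the intercurrent event while OC flares are cut there.* 8.6 is silent on where the time ends; it does not say that it continues.
- *That the censoring rule for time to first flare biases flares per patient-year.* It cannot. It belongs to a separate hazard analysis of an additional endpoint, and its effect there is about 2% under the assumptions tried, less if an SFI is done at discontinuation.

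**What to change.** 1. In SAP 8.5.2, state that the log time-at-risk offset of 8.6 applies to the SFI counts through Week 24 and through Week 48. The reference to 8.5 in 11.2.3 then carries it as well. The Protocol describes the interim analysis as already performed, so record which model was used there.
2. In 8.5.2 and 8.6, define time at risk to match the flares counted. For OC: first dose to the last SFI assessment before the intercurrent event. For AO: first dose to the last SFI assessment in the period.
3. State the rule for subjects with no SFI assessment in the analysed data. SFI is first scheduled at Week 4, so early withdrawals or early intercurrent events have no defined offset. They contribute no time at risk; report their number by arm.
4. Drop visit from the count model in Protocol 7.3, since the response is one total per subject.
5. Minor and separate: in time to first flare, censor every event-free subject at the last SFI assessment in the analysed data, consistent with SAP 8.3.

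The cost is a few sentences in the SAP, and the offset model is already planned for 8.6. Item 4 changes the Protocol. If no amendment is due, the SAP can note that its model replaces the Protocol's. All of this should be fixed before the people who write and run the analysis see treatment assignments.

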8.5.3 Sensitivity and Supplementary Analyses for Secondary Efficacy Endpoints

For all secondary endpoints, analyses using AO data will be performed as additional analyses based on FAS.

8.6 Additional Efficacy Analyses

For the annualized flare rate, a negative binomial regression model will be used with the response variable being the number of flares over the 24-week or 48-week treatment period using both OC and AO data. The model will include covariates of treatment group, and randomization stratification factors. The logarithm (to base e) of the follow-up time will be used as an offset variable in the model to adjust for subjects having different exposure times. The estimated treatment effect and the corresponding 95% CI, as well as the 2-sided p-value will be presented.

A summary of the annualized flare rate by descriptive statistics as well as a summary of the number and percentage of subjects with no flares, at least one flare, 1 flare, 2 flares, and 3 or more flares, respectively, will be presented by treatment group.

Time to event (time to first flare) is defined as number of days from the date of the first dose to the date of the first occurrence of an event. It is calculated as (date of first

occurrence of Event - date of the first dosing + 1). Subjects who discontinue from study prior to experiencing the event are censored at the time of discontinuation. Subjects who are not experiencing the event are censored at the date of last non-missing measurement of SELENA SFI. Data collected on or after the occurrence of intercurrent events as specified in Section 8.2.2 will be excluded. Pairwise comparison between each treatment group and placebo will be performed by log-rank test and Cox proportional hazards regression analysis including treatment and baseline stratification factors as covariates. Same analysis will be performed using AO data as additional analysis.

All other efficacy endpoints specified in Section 3.3 will be analyzed based on FAS using the same approach as that for secondary endpoints as specified in Section 8.5.

8.7 Efficacy Subgroup Analyses

To evaluate the consistency of the efficacy over demographic and other baseline characteristics, subgroup analysis will be performed for the primary endpoint for the subgroups listed in Table 3 below. If any of the resulting subgroups except for age, sex and race has fewer than 5% of the Analysis Population, the subgroup analyses for that category will not be presented.

Point estimate and 95% CI for each treatment group as well as point estimate and 95% CI for treatment differences between treatment groups will be presented using the same analysis method as in the primary analysis. P-value for treatment and subgroup factor interaction using Breslow-Day test will also be provided. In addition:

- A logistic regression with treatment group, subgroup, randomization stratification factors, and treatment by subgroup interaction as factors will be performed to evaluate the significance of the interaction between subgroup and treatment group.
- A stepwise logistic regression with treatment group, all subgroup factors, randomization stratification factors will be performed to evaluate potential important subgroup factor(s).

Table 3. Subgroups

Subgroup Factor	Categories
Age at screening	18 – < 40 years old 40 – < 65 years old ≥ 65 years old
Sex	Male Female
BMI	< 25 ≥ 25
Race	White Black Asian Other
Baseline corticosteroid dose	≤ 10 mg > 10 mg
Screening SLEDAI-2K	< 10 ≥ 10
Baseline immunosuppressant	Yes No
Baseline interferon score	High Low NA
Region	North America/South America, Europe, Asia

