3.7 Biomarker Research

Biospecimens (whole blood, peripheral blood mononuclear cells [PBMCs], plasma, and serum) will be collected at specified time points (Appendix D) throughout the study to evaluate known and/or novel disease-related or drug-related biomarkers. Types of biomarkers may include nucleic acids, proteins, lipids, RNA, DNA, and/or metabolites. The objective of this research is to analyze samples for biomarkers that will help to understand SLE, related conditions, and response to treatment with elsubrutinib, upadacitinib, and ABBV-599 (elsubrutinib/upadacitinib) combination or similar compounds. Research on samples collected in Germany will be limited to SLE, elsubrutinib, upadacitinib, and ABBV-599 (elsubrutinib/upadacitinib) combination. Biomarker samples will not be collected at sites in China as specified in Appendix D.

Type I IFN is a key driver of disease pathogenesis in lupus, and high IFN signature is associated with active SLE.^{10,11} Approximately 60% of lupus patients express an elevated Type I IFN gene signature in the blood, suggesting higher Type I IFN activity in these individuals. JAK1 inhibition is expected to disrupt Type I IFN signaling; therefore, lupus patients expressing the Type I gene signature may be more likely to benefit from treatment with ABBV-599 (elsubrutinib/upadacitinib) combination. A Type I IFN RNA signature consisting of 4 genes (IFI6, IFI27, IFIT1, and MX1) will be evaluated using a validated assay with a cut point set at ≥ -0.25 for IFN high vs < -0.25 for IFN low (-0.25 is the upper limit of the cut point) using the Type I IFN Gene Expression Assay Score. In the event an IFN score cannot be collected or analyzed at Screening due to COVID-19 lab access, that subject will still be enrolled in the study and assigned a score of Not Applicable for the Screening visit. Samples drawn at the Week 4 and Week 24 visits may be used for analysis, if collected.

These results robustly dichotomize the IFN high and low population. The assay will be performed on Screening samples and at subsequent time points unless precluded by local regulations or restrictions (IFN signature samples will not be collected at sites in China). Screening values will be used as a criterion for subject enrichment with the goal of enrolling 80% of the study subjects with high composite score. Stratifying the study to include approximately 80% high IFN score population will allow for increased confidence in the subject population.

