7.7 Sample Size Estimation

The planned sample size for this study is 325 subjects in total, with 65 subjects for each of the 5 groups, determined based on the primary endpoint, the composite of SRI-4 and steroid dose ≤ 10 mg prednisone equivalent QD at Week 24. Assuming at Week 24 the placebo response rate is 25%, a two-sided χ^2 test with $\alpha = 10\%$ will provide 78% to 91% power to detect a difference of 20% to 25% between an active treatment group and the placebo group.

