8.4.2 Main Analysis of Primary Efficacy Endpoint(s)

The attributes of the estimand corresponding to the primary efficacy endpoint are summarized in Table 1.

Table 1. Summary of the Estimand Attributes of the Primary Efficacy Endpoint(s)

Attributes of the Estimand					
Estimand Label	Treatment	Endpoint	Population	Handling of Intercurrent Events	Statistical Summary
Primary	
 Elsubrutinib 60 mg QD and upadacitinib 30 mg QD Elsubrutinib 60 mg QD and upadacitinib 15 mg QD Elsubrutinib 60 mg QD and upadacitinib placebo QD Elsubrutinib placebo QD and upadacitinib 30 mg QD Elsubrutinib placebo QD and upadacitinib placebo QD 	Achievement of SRI-4 and steroid dose ≤ 10 mg prednisone equivalent once a day (QD) at Week 24.	FAS	[REDACTED]	Difference in the percentage of subjects achieving SRI-4 and steroid dose ≤ 10 mg prednisone equivalent once a day (QD) between treatment groups.

The primary analysis of the primary endpoint will be conducted on FAS based on randomized treatment groups (each active treatment group vs placebo) using NRI-C for missing data handling. Point estimate and 95% CI using normal approximation will be provided for the response rate for each randomized treatment group. The difference between the treatment groups in the primary efficacy endpoint will be assessed using the Cochran-Mantel-Haenszel (CMH) test and will be stratified by baseline corticosteroid dose above 10 mg prednisone-equivalent (≤ 10 mg or > 10 mg), screening SLEDAI-2K (< 10 or ≥ 10), baseline interferon score (high or low or not applicable), baseline immunosuppressant (azathioprine, tacrolimus, cyclosporine, methotrexate [MTX], mycophenolate) (yes or no). Baseline interferon score for patients in China will be

considered as not applicable. Point estimate, 95% CI and nominal p-value for the treatment comparison will be presented.

ABBV-599 treatment arms will be compared to the corresponding monotherapy treatment arms, in addition to comparison to placebo. All comparisons or analyses are summarized below,

- Each ABBV-599 vs placebo
- Upadacitinib vs placebo
- Elsubrutinib vs placebo
- Each ABBV-599 vs Elsubrutinib
- Each ABBV-599 vs upadacitinib
- Elsubrutinib 60 mg QD and upadacitinib 30 mg QD vs Elsubrutinib 60 mg QD and upadacitinib 15 mg QD

There will be no multiplicity adjustment for the multiple comparisons.

In the event the study is partially terminated, terminated groups will be removed from the comparisons above.

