12.0 Overall Type-I Error Control

All tests will be performed at two-sided statistical significance level of $\alpha=0.1$. No multiplicity adjustment will be conducted.

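### The interferon interaction p-values in SAP 8.7 include an unmeasured NA group, so they do not isolate the High-versus-Low difference behind the Protocol's enrichment (minor, exploratory)

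*SAP*

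**What the plan says.** SAP 8.7 sets out subgroup analyses of the primary endpoint for the factors in its Table 3. For every factor it gives estimates with confidence intervals by category and then adds: "P-value for treatment and subgroup factor interaction using Breslow-Day test will also be provided". It also plans a logistic regression with a treatment-by-subgroup interaction. Table 3 gives baseline interferon score three categories: High, Low and NA. Section 8.7 neither leaves NA out of the tests nor names a High-versus-Low contrast. One rule limits small groups: apart from age, sex and race, a category holding under 5% of the analysis population is not presented.

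Two kinds of subject fall in NA. SAP 8.4.2 covers the first with a rule that begins "Baseline interferon score for patients in China will be" and ends by coding those patients as not applicable; Protocol 3.7 confirms that no interferon samples are collected in China. The second kind is a subject whose screening score could not be obtained because of COVID-19 lab access. Under Protocol 3.7 that subject is still enrolled and "assigned a score of Not Applicable for the Screening visit".

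Protocol 3.7 also explains the interest in the score: "lupus patients expressing the Type I gene signature may be more likely to benefit from treatment with ABBV-599". It sets a goal of 80% High subjects, and the score is a randomization stratum.

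**The concern.** The biomarker question in Protocol 3.7 is whether High subjects benefit more than Low subjects. The NA subjects are an unknown mix of the two, grouped by country or by a logistical failure. With NA as a third level, the p-value labelled interferon asks whether the treatment effect is the same in High, Low and unmeasured subjects.

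That has two consequences. A different effect in China or in the missing-sample group can appear as an interferon interaction when High and Low benefit equally. And a true High-versus-Low difference is tested with a degree of freedom spent on NA. The trial is meant to inform dose choice and the next studies, so a misread biomarker signal could carry forward.

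**Working it through.** **Inputs from the documents.** Protocol 7.7: "325 subjects in total, with 65 subjects for each of the 5 groups"; "Assuming at Week 24 the placebo response rate is 25"%; "78% to 91% power to detect a difference of 20% to 25"%. SAP 12.0: "All tests will be performed at two-sided statistical significance level of" 0.1, with no multiplicity adjustment. SAP Table 3: three interferon categories.

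**Inputs assumed.** The documents give no NA count, so the NA share is varied over 5%, 10% and 20% per arm. High:Low is 4:1 among subjects with a score, following the 80% goal.

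**Step 1: reproduce the plan's own power.** With n = 65 per group and p̄ the mean of the two rates, power = Φ{[√n·|p2 − p1| − 1.645·√(2p̄(1 − p̄))] / √(p1(1 − p1) + p2(1 − p2))}.

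- 25% vs 45%: (1.612 − 1.110)/0.660 = 0.763, power 77.7% (plan: 78%).
- 25% vs 50%: (2.016 − 1.126)/0.661 = 1.345, power 91.1% (plan: 91%).

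The planning figures reproduce, so the same setting is used below.

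**Step 2: what each test measures.** For one active group against placebo, Breslow-Day is X² = Σ(a − E)²/V over interferon categories. Here a is the number of active responders, and E and V are its expectation and variance under the Mantel-Haenszel common odds ratio. It has 2 df with High, Low and NA, and 1 df with High and Low. In a logistic model with all five groups, the interaction has 4 × 2 = 8 df instead of 4 × 1 = 4. The count falls if terminated groups are removed.

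**Step 3: two constructed tables** (per arm: High 42, Low 10, NA 13).

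- *NA creates the signal.* Responders on active are 21/5/2 and on placebo 11/3/6 (High/Low/NA). The odds ratios are (21·31)/(21·11) = 2.82 in High, (5·7)/(5·3) = 2.33 in Low and (2·7)/(11·6) = 0.21 in NA. Three-level X² = 6.80, p = 0.033; High vs Low X² = 0.03, p = 0.86.
- *NA hides the signal.* Responders on active are 23/3/6 and on placebo 10/4/3. Three-level X² = 3.02, p = 0.22; High vs Low X² = 3.01, p = 0.083, which is below 0.10.

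These show what can happen, not how often.

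**Step 4: how often, with no High-versus-Low difference.** Simulated at 65 vs 65 and alpha 0.10, with placebo 25% throughout and active 50% in both High and Low. Ranges cover NA shares of 5% to 20%. Separate runs agree within one or two points.

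| Active response in NA | Three-level test rejects | High vs Low rejects |
|---|---|---|
| 50% (same benefit) | 10-11% | 10-12% |
| 35% (partial benefit) | 13-16% | 10-12% |
| 25% (no benefit) | 17-26% | 10-12% |
| 15% (worse than placebo) | 21-42% | 10-12% |

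**Step 5: with a real difference.** Active 55% in High, 20% in Low and 40% in NA. At NA shares of 5%, 10% and 20%, power for High vs Low is 46%, 46% and 41%; with NA included it is 42%, 40% and 37%. The loss is 46 − 42 = 4, 46 − 40 = 6 and 41 − 37 = 4 points. In a stronger case (High 60%, Low 15%, NA 51%; NA share 5% to 25%), power falls from 58-63% to 50-56%, a loss of 7 to 8 points.

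**Step 6: reach of the 5% rule.** 5% of 325 is 16.25, so with all five groups counted NA is presented from 17 subjects upward. Below that it is not presented, but the SAP does not say whether it also leaves the interaction test.

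**The case against.** SAP 8.7 describes its purpose as checking that efficacy is consistent across baseline characteristics. NA is a level of the randomization factor, so a test over all three levels does what the section says, and a different effect in NA is real heterogeneity rather than a false positive. This stands as far as it goes. But Table 3 already has separate race and region factors, where heterogeneity of that kind belongs, and a p-value labelled interferon will be read as being about interferon.

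Several limits on the point also stand. High, Low and NA estimates are shown separately, so a reader can see what NA does. A three-level logistic model contains a High-versus-Low term, although the SAP does not name it as the test. SAP 1.0 sends biomarker analyses to a separate document, which may hold a dedicated contrast. The larger NA shares are speculative: 20% NA with High:Low at 4:1 leaves only 0.8 × 0.8 = 64% of subjects High, against the 80% goal.

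A reader might infer that the plan fails to test one of the trial's hypotheses. The documents do not support that. The formal hypotheses in Protocol 3.1 and SAP 2.1 contain no interferon contrast. The statement in Protocol 3.7 is a rationale, worded for the combination. A reader might also infer that the test gives spurious interactions in up to 42% of trials. That figure requires response in NA to be lower on active treatment than on placebo, which nothing in the documents suggests.

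**Conclusion.** The point holds as a minor one about an exploratory p-value. As written, both interferon interaction tests run over High, Low and NA. That reading rests on Table 3 and the absence of any exclusion, since no sentence says so outright. The result therefore does not isolate the High-versus-Low difference.

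The size depends on how NA subjects respond, which is unknown. If they respond like the others, the rejection rate stays at about 10-11% and the only cost is power. A partial or absent benefit in NA raises it to 13-16% or 17-26%. The power loss is about 4 to 6 points in the main scenario and 7 to 8 in the stronger one. In the main scenario the High-versus-Low test has under 50% power even without NA, so the gain is mainly a p-value that matches its label. All of this assumes 65 per group, the Protocol's 25% placebo rate and NA shares that the documents do not give.

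It would be wrong to infer that the primary analysis is affected. Keeping NA as a stratum in the CMH test is not the problem, and no decision rule in the documents depends on this p-value.

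**What to change.** Add one sentence to SAP 8.7: for baseline interferon score, the Breslow-Day and logistic interaction p-values are computed on High and Low subjects only, and NA results are shown descriptively whatever the size of that group relative to the 5% rule. This also settles what the rule does to the interferon test.

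The cost is that NA subjects do not contribute to this one exploratory comparison. They stay in the displayed estimates, in the other subgroup factors and in the primary analysis, where the NA stratum is unchanged.
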